10.3 Response Criteria for Patients with Solid Tumors (non-CNS)

Response and progression will be evaluated in this study using the revised Response Evaluation Criteria in Solid Tumors (RECIST) guideline (version 1.1).⁵¹ Key points are that 5 target lesions are identified and that changes in the *largest* diameter (unidimensional measurement) of the tumor lesions are used in the RECIST v 1.1 criteria.

10.3.1 Measurable Disease

The presence of at least one lesion that can be accurately measured in at least one dimension with the longest diameter at least 10 mm (CT scan slice thickness no greater than 5 mm). The investigator will identify up to 5 measurable lesions to be followed for response. Patients with previously irradiated lesions are not eligible for Cohorts A and B of this protocol.

Serial measurements of lesions are to be done with appropriate imaging modalities, e.g., CT or MRI. Bone scans cannot be used to measure lesions. The same method of assessment is to be used to characterize each identified and reported lesion at baseline and during follow-up. All tumor measurements must be recorded in millimeters (or decimal fractions of centimeters).

10.3.2 Quantification of Disease Burden

The sum of the longest diameter (LD) for all target lesions will be calculated and reported as the disease measurement.

10.3.3 End-of-Cycle Response

Note: Please also see Table 1 in [Section 10.4](#).

a) Complete Response (CR)

Disappearance of all target and non-target lesions. Normalization of urinary catecholamines (for patients with neuroblastoma), immunocytologic findings, or other tumor markers if abnormal or elevated at study enrollment.

b) Partial Response (PR)

At least a 30% decrease in the disease measurement, taking as reference the disease measurement done to confirm measurable disease at study enrollment. No new lesions or progression of any non-target measurable lesion.

c) Stable Disease (SD)

Neither sufficient shrinkage to qualify for PR nor sufficient increase to qualify for PD taking as reference the smallest disease measurement since the treatment started.

d) Progressive Disease (PD)

At least a 20% increase in the sum of the disease measurements for measurable lesions, taking as reference the smallest disease measurement recorded since the start of treatment, or the appearance of one or more new lesions.

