10.5 Response Criteria for Patients with CNS Tumors

10.5.1 Selection of Target and Non-Target Lesions

For most CNS tumors, only one lesion/mass is present and therefore is considered a "target" for measurement/follow up to assess for tumor progression/response. If multiple measurable lesions are present, up to 5 should be selected as "target" lesions. Target lesions should be selected on the basis of size and suitability for accurate repeated measurements. All other lesions will be followed as non-target lesions. The lower size limit of the target lesion(s) should be at least twice the thickness of the slices showing the tumor to decrease the partial volume effect (e.g., 8 mm lesion for a 4 mm slice).

Any change in size of non-target lesions should be noted, though does not need to be measured.

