10.5.2 Response Criteria for Target Lesions

Response criteria are assessed based on the product of the longest diameter and its longest perpendicular diameter. Development of new disease or progression in any established lesions is considered progressive disease, regardless of response in other lesions – e.g., when multiple lesions show opposite responses, the progressive disease takes precedence. Response Criteria for target lesions:

- **Complete Response (CR):** Disappearance of all target and non-target lesions.
- **Partial response (PR):** $\geq 50\%$ decrease in the sum of the products of the two perpendicular diameters of all target lesions (up to 5), taking as reference the initial baseline measurements.
- **Stable Disease (SD):** Neither sufficient decrease in the sum of the products of the two perpendicular diameters of all target lesions to qualify for PR, nor sufficient increase in a single target lesion to qualify for PD.
- **Progressive Disease (PD):** 25% or more increase in the product of perpendicular diameters of ANY target lesion, taking as reference the smallest product observed since the start of treatment, or the appearance of one or more new lesions.

10.5.3 Response Criteria for Non-Target Lesions:

- **Complete Response (CR):** Disappearance of all non-target lesions.
- **Incomplete Response/Stable Disease (IR/SD):** The persistence of one or more non-target lesions.
- **Progressive Disease (PD):** The appearance of one or more new lesions and/or unequivocal progression of existing non-target lesions.

10.5.4 Response criteria for tumor markers (if available):

Tumor markers will be classified simply as being at normal levels or at abnormally high levels.

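### The written progression rule for non-CNS solid tumors leaves out growth of existing non-target lesions, in conflict with the partial-response rule beside it and with the CNS rule

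*Combined protocol and SAP*

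**What the plan says.** All references are to the combined protocol and SAP.

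- **Disease measurement (10.3.2):** "The sum of the longest diameter (LD) for all target lesions will be calculated and reported as the disease measurement".
- **PD outside the CNS (10.3.3(d)):** the first route reads "At least a 20% increase in the sum of the disease measurements for measurable lesions, taking as reference the smallest disease measurement recorded since the" treatment began; the second is any new lesion. Existing non-target lesions are not mentioned, and no minimum increase in millimeters is set.
- **PR (10.3.3(b)):** a fall of at least 30% from baseline, with the condition "No new lesions or progression of any non-target measurable lesion".
- **Stable disease (10.3.3(c)):** requires both too little shrinkage for PR and too little increase for PD.
- **CNS tumors (10.5.3):** PD in non-target lesions is "The appearance of one or more new lesions and/or unequivocal progression of existing non-target lesions". The table in 10.5.5 carries this to overall PD whatever the target lesions do.
- **Measurable disease (10.3.1):** at least one lesion "with the longest diameter at least 10 mm (CT scan slice thickness no greater than 5 mm"), with up to five lesions followed.
- **Governing text:** Section 10.3 says response and progression follow RECIST 1.1. Sections 4.3.2 and 7.1 let the investigator call progression on clinical or laboratory grounds. Section 8.1(a) accepts clinical or radiographic evidence but refers back to 10.3.3 for the definition.
- **Use of PD:** it is the event for duration of response (9.3), it enters the progression endpoints listed there, and it ends protocol therapy (4.1.3.4).

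**The concern.** The PR rule treats growth of a measurable non-target lesion as serious enough to deny a response. The CNS rule treats any unequivocal non-target growth as progression. The non-CNS PD rule does neither. Two patients are then handled badly. One has shrinking targets and a growing measurable non-target lesion, and fits no category. The other has shrinking targets and growing non-measurable disease, and is scored as a responder.

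The patients concerned can enroll. Section 4.1.3.2 provides for metastatic disease, Section 3.2.6.1 admits solid tumors with marrow metastases, and Section 10.3.1 does not let bone scans serve as measurements. What is at stake is mainly the date of PD. If non-target progression is missed, duration of response and time to progression are too long in the patients with the most disease.

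**Working it through.** **1. The plan's own figures.** The plan gives no millimeter figure for PD. The related figures are the Simon operating characteristics in 9.2: 9 then 12 patients, stop at 5 or fewer responses, effective at 16 or more of 21. With P(effective | p) = Σ over x = 6 to 9 of Bin(x; 9, p) × P[Bin(12, p) ≥ 16 − x]:

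| Quantity | Stated | Recomputed |
|---|---|---|
| Type I error, p = 0.60 | 9.05% | 9.05% |
| Power, p = 0.85 | 90.40% | 90.40% |
| Early termination, p = 0.60 | 51.74% | 51.74% |
| Expected N, p = 0.60 | 14.8 | 14.79 |

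These do not depend on the PD wording and are correct.

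**2. Measurable non-target growth (illustrative sizes).** The target sum goes from 100 to 60 mm while a measurable non-target lesion goes from 20 to 40 mm, with no new lesion.

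- PR: (100 − 60)/100 = 40%, so the size condition is met, but 10.3.3(b) bars PR.
- PD: the target sum has not risen from its nadir and there is no new lesion, so PD is not met.
- Stable disease: shrinkage is already enough for PR, so the literal wording is not met.

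The wording in (d) about measurable lesions could be read to add the non-target lesion. The total is then 100 + 20 = 120 mm falling to 60 + 40 = 100 mm, which is still not PD.

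**3. Non-measurable non-target growth.** With the same targets and a growing effusion or bone disease, the exclusion in 10.3.3(b) covers only measurable non-target lesions. The patient is PR and not PD. Under 10.5.3 and 10.5.5 the equivalent CNS patient is PD.

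**4. Where this lands.** Under 9.4, anyone without a centrally confirmed CR or PR is a non-responder, so the patient in step 2 is a non-responder under either rule. Only the patient in step 3 could raise the response rate. One patient in 21 is 1/21 = 4.8 percentage points. The documents give no frequency. As an assumption, suppose 2%, 5% or 10% of true non-responders at p = 0.60 were scored as responders. The rate becomes 0.60 + 0.40m = 60.8%, 62.0% or 64.0%, and the chance of declaring the drug effective rises from 9.05% to 10.3%, 12.4% or 16.6%. For Cohort A the low end or below is the likely region, because Section 2.1.2 describes infantile fibrosarcoma as almost always localized.

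**5. Secondary point: no absolute minimum.** The PD trigger in millimeters is 0.20 × nadir sum.

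| Nadir sum (mm) | Increase reaching PD (mm) |
|---|---|
| 5 | 1.0 |
| 10 | 2.0 |
| 25 | 5.0 |
| 50 | 10.0 |

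The 1 to 2 mm case needs a nadir sum of 5 to 10 mm, which means shrinkage of 80 to 90% from a 50 mm baseline or 90 to 95% from 100 mm. Below a 25 mm nadir the trigger is smaller than the 5 mm maximum slice thickness in 10.3.1.

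**The case against.** The strongest reply is that Section 10.3 adopts RECIST 1.1 and then lists key points, so 10.3.3 may be only an abridgement and the missing element may come from the guideline. This is a fair reading, and the guideline is not reproduced here to test it. But 8.1(a) sends the reader to 10.3.3, and no section says which text prevails where they differ. The reply weakens the point to a need for reconciliation; it does not remove it.

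Second, a worsening effusion or marrow disease could be called progression on clinical or laboratory grounds under 4.3.2 and 7.1. That stands: it would be wrong to say such growth can never be recorded as PD. It leaves the call to individual judgment, while central review of imaging through Cycle 6 (7.4) needs a written rule.

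Third, the primary endpoint is barely touched. This largely stands, for the reasons in step 4 of the working.

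Fourth, on the missing minimum increase, the CNS rule has none either, so the documents do not contradict themselves there. They give no baseline sizes or depth of shrinkage from which to derive how often tiny nadirs occur. A 5 mm floor would be a preference taken from a CT slice limit, which is not the error of a diameter reading, and MRI is also allowed. All of this stands, and it is why the point is secondary.

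Fifth, accrual is complete and activity has been reported (2.7.1), so a changed definition could look post hoc. That argues for showing openly which patients change. Follow-up runs to five years from enrollment (8.2(e)), so progression dates can still accrue.

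**Conclusion.** The inconsistency is real and lies in the text: 10.3.3(d) omits what 10.3.3(b) partly recognizes and 10.5.3 fully recognizes. Its likely effect is to lengthen duration of response and the progression endpoints in multi-lesion or metastatic patients, chiefly in Cohort B. Its size cannot be derived, because the documents do not say how many patients had non-target disease. Event-free survival is named in the aims but not defined in 9.3, so any effect on it is an inference.

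A reader might infer more than the documents support:

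- **That the Cohort A response rate is inflated or the design figures are wrong.** The Simon figures reproduce, and the inflation needs growing non-measurable disease in a tumor that is almost always localized.
- **That false PD is common in deep responders.** The 1 to 2 mm arithmetic is right but applies only to nadir sums of 5 to 10 mm, and their frequency is unknown. Turning a PR into a best response of PD under 10.4 would also need the tiny nadir at the first scan and apparent regrowth by the second.
- **That a 5 mm floor, or a minimum size for CNS lesions, should be imposed.** Nothing in the documents anchors either.

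The conclusion rests on reading 10.3.3 literally, which 8.1(a) invites.

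**What to change.** 1. Reconcile 10.3.3(b) and (d) with 10.5.3 and with the RECIST 1.1 citation in 10.3, and state which text governs.
2. For endpoint classification, treat unequivocal progression of any existing non-target lesion, measurable or not, as PD and as incompatible with PR.
3. Apply this to duration of response and the progression dates using the imaging and clinical reports on file. The recorded target sums are not enough, because 10.3.2 excludes non-target lesions from them. List every patient whose category or date changes.
4. On the secondary point, confirm whether the cited guideline sets a minimum absolute increase that applies here, and report how many PD calls rest on an increase below 5 mm.
5. Because PD also ends protocol therapy (4.1.3.4), the sponsor must reconcile that link with the clarified text. No stopping rule is proposed here.

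The cost is a wording clarification and some retrospective review of non-target findings. Duration of response may become slightly shorter. Patients already removed for PD follow the sparser schedule in 7.2, so some later dates may not be recoverable.

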10.3.4 Overall Best Response Assessment

Each patient will be classified according to their “best response” for the purposes of analysis of treatment effect. For this analysis, the best response refers to the

response to larotrectinib only and not surgical resection. Best response is determined from the sequence of the objective statuses described in [Section 10.4](#).

10.4 Best Response (Solid Tumors)

Two objective status determinations of disease status, by CT or MRI, obtained on two consecutive determinations, separated by at least a 3 week time period, are required to determine the patient's overall best response. Two objective status determinations of CR before progression are required for best response of CR. Two determinations of PR or better before progression, but not qualifying for a CR, are required for a best response of PR. Two determinations of stable/no response or better before progression, but not qualifying as CR or PR, are required for a best response of stable/no response; if the first objective status is unknown, only one such determination is required. Patients with an objective status of progression on or before the second evaluations (the first evaluation is the first radiographic evaluation after treatment has been administered) will have a best response of progressive disease. Best response is unknown if the patient does not qualify for a best response of progressive disease and if all objective statuses after the first determination and before progression are unknown.

Table 1: Sequences of objective statuses with corresponding best response.

| 1 st Status | 2 nd Status | 3 rd Status | Best Response |
|------------------------|------------------------|------------------------|---------------------|
| Progression | | | Progressive disease |
| Stable, PR, CR | Progression | | Progressive disease |
| Unknown | Progression | | Progressive disease |
| Stable | Stable | Progression | Stable |
| Stable, Unknown | PR, CR | Progression | Stable |
| Stable, Unknown | Unknown | Progression | Unknown |
| PR | PR | Progression | PR |
| PR | CR | Progression | PR |
| PR, CR | Unknown | Progression | Unknown |
| CR | CR | Progression | CR |
| Unknown | Stable | Progression | Stable |

10.5 Response Criteria for Patients with CNS Tumors

10.5.1 Selection of Target and Non-Target Lesions

For most CNS tumors, only one lesion/mass is present and therefore is considered a "target" for measurement/follow up to assess for tumor progression/response. If multiple measurable lesions are present, up to 5 should be selected as "target" lesions. Target lesions should be selected on the basis of size and suitability for accurate repeated measurements. All other lesions will be followed as non-target lesions. The lower size limit of the target lesion(s) should be at least twice the thickness of the slices showing the tumor to decrease the partial volume effect (e.g., 8 mm lesion for a 4 mm slice).

Any change in size of non-target lesions should be noted, though does not need to be measured.

10.5.2 Response Criteria for Target Lesions

Response criteria are assessed based on the product of the longest diameter and its longest perpendicular diameter. Development of new disease or progression in any established lesions is considered progressive disease, regardless of response in other lesions – e.g., when multiple lesions show opposite responses, the progressive disease takes precedence. Response Criteria for target lesions:

- **Complete Response (CR):** Disappearance of all target and non-target lesions.
- **Partial response (PR):** $\geq 50\%$ decrease in the sum of the products of the two perpendicular diameters of all target lesions (up to 5), taking as reference the initial baseline measurements.
- **Stable Disease (SD):** Neither sufficient decrease in the sum of the products of the two perpendicular diameters of all target lesions to qualify for PR, nor sufficient increase in a single target lesion to qualify for PD.
- **Progressive Disease (PD):** 25% or more increase in the product of perpendicular diameters of ANY target lesion, taking as reference the smallest product observed since the start of treatment, or the appearance of one or more new lesions.

10.5.3 Response Criteria for Non-Target Lesions:

- **Complete Response (CR):** Disappearance of all non-target lesions.
- **Incomplete Response/Stable Disease (IR/SD):** The persistence of one or more non-target lesions.
- **Progressive Disease (PD):** The appearance of one or more new lesions and/or unequivocal progression of existing non-target lesions.

10.5.4 Response criteria for tumor markers (if available):

Tumor markers will be classified simply as being at normal levels or at abnormally high levels.

10.5.5 Overall Response Assessment

The overall response assessment takes into account response in both target and non-target lesions, the appearance of new lesions and normalization of markers (where applicable), according to the criteria described in the table below. The overall response assessment is shown in the last column, and depends on the assessments of target, non-target, marker and new lesions in the preceding columns.

| Target Lesions | Non-target Lesions | Markers | New Lesions | Overall Response |
|----------------|--------------------|----------|-------------|------------------|
| CR | CR | Normal | No | CR |
| CR | IR/SD | Normal | No | PR |
| CR | CR, IR/SD | Abnormal | No | PR |

| | | | | |
|-----|-----------|-----|-----------|----|
| PR | CR, IR/SD | Any | No | PR |
| SD | CR, IR/SD | Any | No | SD |
| PD | Any | Any | Yes or No | PD |
| Any | PD | Any | Yes or No | PD |
| Any | Any | Any | Yes | PD |

Each patient will be classified according to his “best response” for the purposes of analysis of treatment effect. Best response is determined as outlined in [Section 10.4](#) from a sequence of overall response assessments.

10.6 Response Criteria for Patients with AML

The AML response criteria are derived from the revised AML International Working Group (IWG) Criteria.⁵²

10.6.1. Complete Remission (CR)

Attainment of an M1 bone marrow (< 5% blasts) with no evidence of circulating blasts or extramedullary disease and with recovery of peripheral blood counts (ANC $\geq 1000/\text{mm}^3$ and platelet count $\geq 100,000/\text{mm}^3$). Occasionally, a rare peripheral blood blast may be identified during marrow regeneration; however, the marrow must be M1 status and with no Auer rods. Flow cytometry may also be useful to distinguish between leukemia and a regenerating bone marrow. There is no requirement for bone marrow cellularity.

10.6.2 CR With Partial Recovery of Platelet Count (CRp)

Attainment of an M1 bone marrow (< 5% blasts) with no Auer rods, no evidence of circulating blasts or extramedullary disease and with recovery of ANC $\geq 1000/\text{mm}^3$ and platelet transfusion independence (defined as: no platelet transfusions x 1 week).

10.6.3 CR with incomplete blood count recovery (CRi)

Attainment of an M1 bone marrow (< 5% blasts) with no Auer rods, no evidence of circulating blasts or extramedullary disease and with ANC $< 1000/\text{mm}^3$ or platelet count $< 100,000/\text{mm}^3$ without platelet transfusion independence (defined as: no platelet transfusions x 1 week).

10.6.4 Cytogenetic Complete Remission (CRc)

The patient must also have attained and be assigned to response of morphologic CR or CRp or CRi as defined above. In addition, reversion to a normal karyotype with a minimum analysis of 20 metaphases.

10.6.5 Partial Response (PR)

A decrease of at least 50% in the percentage of blasts to 5% to 25% in the bone marrow aspirate. Bone marrow must have adequate cellularity (e.g., > 15%) to determine response. PR status will not be included in calculation of response to the regimen. A repeat bone marrow aspiration after several weeks may be required to distinguish between a PR and increased blasts caused by bone marrow regeneration. A value of < 5% blasts may also be considered a PR if Auer rods are present.

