1.3 Exploratory Aims

- 1.3.1 To determine the EFS, OS, and DoR of children with TRK fusion solid tumors other than IFS treated with adjuvant larotrectinib following upfront surgery with positive margins after neoadjuvant larotrectinib.
- 1.3.2 To determine the EFS, OS, and DoR of children with TRK fusion solid tumors who experience a complete response to larotrectinib and subsequently discontinue larotrectinib therapy
- 1.3.3 To determine the remission induction rate for patients with recurrent/refractory TRK fusion leukemia when treated with larotrectinib.
- 1.3.4 To evaluate the surgical morbidity and extent of resection of initially unresectable tumors in patients with TRK fusion solid tumors who undergo surgical resection following neoadjuvant larotrectinib.
- 1.3.5 To evaluate mechanisms of response and resistance to larotrectinib in children with TRK fusion cancers.
- 1.3.6 To evaluate the morphologic features of TRK fusion solid tumors at time of initial

biopsy to further define criteria for pathologic diagnosis of these tumors.

- 1.3.7 To evaluate immunohistochemistry for pan-TRK as a screening method for TRK fusion tumors and in resection specimens following neoadjuvant treatment with larotrectinib.
- 1.3.8 To evaluate the histologic response to larotrectinib in resection specimens following neoadjuvant treatment.
- 1.3.9 To evaluate circulating tumor DNA for the detection of the emergence of resistance mutations and recurrence in patients with TRK fusion solid tumors treated with larotrectinib.
- 1.3.10 To evaluate the ratio of CSF to concurrent plasma concentrations of larotrectinib in patients with leukemia.
- 1.3.11 To evaluate the change in neurocognitive/behavioral functioning over time between baseline and 5 years post-diagnosis of patients treated on this protocol using parent-reported adaptive functioning (ABAS-III General Adaptive Composite), executive function (BRIEF-P or BRIEF-2 Global Executive Composite Score), psychosocial functioning (BASC-3 Internalizing, Externalizing and Behavioral Symptoms Indices) and quality of life (PedsQL Total score).

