9.3 Methods of Analysis

Response criteria are described in [Section 10.2](#). A responder is defined as a patient who achieves a best response (as defined in [Section 10.3.4](#)) of PR or CR on the study. Response rates will be calculated as the percent of evaluable patients who are responders, and confidence intervals will be constructed accounting for the two-stage design.

Toxicity tables will be constructed to summarize the observed incidence by type of toxicity and grade. A patient will be counted only once for a given toxicity for the worst grade of that toxicity reported for that patient. Toxicity information recorded will include the type, severity, time of onset, time of resolution, and the attribution(s) to the study regimen.

Time-to-event analyses (time to progression, progression-free survival, overall survival, and duration of response) will be computed one year after the last enrollment in a stratum. Duration of response will be defined among patients with a confirmed best response of either PR and CR, and will be defined as the time from the first observation of either PR or CR until either the first observation of PD (event) or last known observation of the patient (censored observation).

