10.7.4 Stable Disease (SD)

Patient does not satisfy the criteria for PD, or has recovery of ANC $\geq 500/\mu\text{L}$ and fails to qualify for CR, CRI, or PR.

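### Sections 9.3 and 9.4 apply a solid-tumor responder definition to every cohort, which contradicts the AML rule in 10.6.5 and the disease-specific routing in 9.2 and 10.2

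*Combined protocol and SAP*

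**What the plan says.** **Responder definition.** Section 9.3 reads: "A responder is defined as a patient who achieves a best response (as defined in [Section 10.3.4](#)) of PR or CR on the study". It carries no restriction to solid tumors. The cited section, 10.3.4, belongs to the non-CNS solid-tumor criteria and hands over to 10.4: "Best response is determined from the sequence of the objective statuses described in" that section. Section 10.4 then requires "Two objective status determinations of disease status, by CT or MRI", consecutive and at least three weeks apart. Section 9.4 counts a centrally confirmed CR or PR as a response when the two-stage rule is applied, makes everyone else a non-responder, and requires central imaging review for every CR or PR.

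**Leukemia criteria.** Section 9.2 bases the endpoint on disease-specific criteria, and 10.2 assigns AML to 10.6 and ALL to 10.7. Those sections rest on marrow blasts, circulating blasts, extramedullary disease and blood counts. On AML partial response, 10.6.5 says "PR status will not be included in calculation of response to the regimen". CRp and CRi are separate categories for AML (10.6.2, 10.6.3), as is CRi for ALL (10.7.2).

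**Aim.** The leukemia aim, 1.3.3, is exploratory: "To determine the remission induction rate for patients with recurrent/refractory TRK fusion leukemia". Section 9 does not define that rate.

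**ALL stable disease.** Section 10.7.4 begins "Patient does not satisfy the criteria for PD, or has recovery of ANC" at or above 500/µL, and the second limb then adds failing to qualify for CR, CRi or PR.

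**The concern.** Two instructions govern the same numerator. An analyst working from 9.3 and 9.4 counts an AML partial response; an analyst working from 10.6.5 does not. The cross-reference adds a second problem. A rule built on pairs of CT or MRI scans cannot classify a patient whose disease is measured in the marrow, and central imaging review cannot confirm a marrow remission. Section 4.5.2 repeats the misdirection by sending Cohort C to 10.4 for RECIST confirmation.

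At stake is the one efficacy figure planned for the leukemia cohort. Because the remission induction rate has no stated numerator, the reported value could be chosen after the data are seen. Under 9.1, observed response rates in the secondary strata also feed the decision on keeping those strata open, and the two-stage rule could apply to a leukemia histology if enough patients enrolled.

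**Working it through.** **1. The design figures are sound.** With p the true response rate, the rule (at least 6 of 9, then at least 16 of 21) gives:

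- P(declared effective) = Σ over x = 6 to 9 of C(9,x) pˣ(1−p)⁹⁻ˣ × P(Bin(12,p) ≥ 16−x)
- At p = 0.60: 0.0905 (plan: 9.05%). At p = 0.85: 0.9040 (plan: 90.40%)
- P(early termination at 0.60) = P(Bin(9, 0.60) ≤ 5) = 0.5174 (plan: 51.74%)
- Expected N at 0.60 = 9 + 12 × (1 − 0.5174) = 14.79 (plan: 14.8)

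All reproduce. The problem is what counts as a response, not the rule.

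**2. The two routes side by side.**

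| Leukemia patient | 9.3 and 9.4 as written | 9.2 → 10.2 → 10.6/10.7 |
|---|---|---|
| AML, best status PR | Responder by the words used | Not counted (10.6.5) |
| AML or ALL, marrow CR, no imaging lesion | No scan pair under 10.4 and no imaging to confirm centrally | CR |
| AML, CRp or CRi | Not named | Titled as forms of CR; not said to count |
| ALL, CRi | Not named | Titled as a complete response; not said to count |
| ALL, PR | Responder by the words used | 10.7.3 has no exclusion |

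The first row is a direct contradiction. The second is a cross-reference that does not fit the disease. The third and fourth are silence. The fifth is no conflict.

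**3. Size for a descriptive rate.** One reclassified patient shifts the rate by 1/n. The plan gives no Cohort C projection, so n is assumed: n = 3 gives 33.3 points, n = 5 gives 20.0, n = 9 gives 11.1.

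**4. Size if the two-stage rule were ever reached.** Section 9.1 requires nine response-evaluable patients of one histology first. The AML rates below are assumptions, not figures from the documents. Entries are P(declared effective) from the formula in step 1.

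| Assumed CR / PR / CRp+CRi | CR + PR (words of 9.3) | CR + CRp/CRi, no PR | CR only |
|---|---|---|---|
| 30% / 30% / 25% | 9.05% | 3.66% | <0.01% |
| 40% / 20% / 20% | 9.05% | 9.05% | 0.08% |
| 50% / 15% / 20% | 19.09% | 34.71% | 1.25% |
| 60% / 10% / 15% | 34.71% | 54.69% | 9.05% |

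The choice between 9.3 and 10.6.5 can push the result either way or not at all. Whether CRp and CRi count matters in every row.

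**5. ALL stable disease.** As worded, SD = (not PD) *or* (ANC ≥ 500/µL and not CR, CRi or PR).

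- A patient in CR, CRi or PR without PD meets the first limb.
- A patient with PD, recovered ANC and none of CR, CRi or PR meets the second limb, because 10.7.5 allows PD whether or not counts recover.
- With *and* in place of *or*, a patient with an M2 marrow, ANC below 500/µL and no PD fits no category.
- With SD defined as meeting none of CR, CRi, PR or PD, both the overlap with SD and the gap disappear.

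**The case against.** The best defense is that the routing exists elsewhere. Section 9.3 opens by pointing to 10.2, which sends AML to 10.6 and ALL to 10.7, and 9.2 speaks of disease-specific criteria. If the specific sentence overrides the general one, AML PR is excluded and 9.3 contains only a stray cross-reference. That is a reasonable guess at intent. It does not remove the conflict, because 9.4 repeats PR or CR, labels everyone else a non-responder, and ties confirmation to imaging, again without a cohort limit.

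Other parts of the defense stand, and they rule out stronger readings that a reader might infer:

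- *That the plan drops CRp and CRi patients from response.* The documents do not say so. Their titles make them forms of CR, 10.6.4 accepts CR, CRp or CRi as the basis for cytogenetic remission, and 10.6.7 defines relapse after any of the three. The point is unstated, not contradicted.
- *That the 6-of-9 and 16-of-21 cutoffs will be applied to leukemia.* They apply only once nine evaluable patients of one histology enroll. Section 2.1.5 calls these fusions rare, and 2.7.1 reports that accrual is complete.
- *That the overlap in 10.7.4 distorts the response rate or keeps patients with PD on treatment.* SD and PD are both non-response, a patient in CR still meets CR, and 8.1(a) makes PD under 10.7.5 a removal criterion in its own right.
- *That ALL PR must also be excluded.* Only the AML section has such a sentence.

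**Conclusion.** The contradiction is real: 9.3 and 9.4 cannot be applied to AML together with 10.6.5, and their imaging rules do not fit either leukemia. The correction is worth making because the numerator of aim 1.3.3 is otherwise open.

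The reach is narrow. It covers Cohort C, which is exploratory and reported descriptively. The primary endpoint in Cohort A, the solid-tumor analysis in Cohort B and all stated design figures are unaffected. The size is 1/n per reclassified patient. The documents do not give the number of leukemia patients enrolled; if there were none, nothing in the results changes. The two-stage probabilities above rest on assumed AML rates and on a condition that may never have been met, so they illustrate sensitivity only.

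The overlap in 10.7.4 is a secondary drafting fault, with no shown effect on the response rate.

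**What to change.** 1. In 9.3 and 9.4, limit the 10.3.4/10.4 definition and the central imaging confirmation to Cohorts A and B.
2. For Cohort C, cite 10.6 (AML) and 10.7 (ALL). Exclude AML PR from the response count, as 10.6.5 already does.
3. Define the remission induction rate of aim 1.3.3 and state that CRp and CRi (AML) and CRi (ALL) count toward it, in line with 10.6.4 and 10.6.7. Report ALL PR on its own line and leave its inclusion to the sponsor.
4. Remove the pointer to RECIST confirmation for Cohort C in 4.5.2.
5. Reconcile 10.7.4 with 10.7.1–10.7.3 and 10.7.5, so that SD means meeting none of CR, CRi, PR or PD. Swapping *or* for *and* is not enough, because it leaves some patients unclassified.

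The cost is a few sentences, with no new data, no change in sample size and no effect on Cohorts A or B. The wording should be settled before the Cohort C response rate is tabulated or, if that has already happened, the report should state which definition was used.
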